### 3.2 Study procedures including recruitment and data-collection

The main outcomes of this study are gathered on the days of OPU and Embryo transfer as presented in figure 1.

[figure not shown]

Figure 1: Study procedure and data collection for participating couples of the GAP-RCT

**On the day of their oocyte aspiration**, couples will be informed on the study and asked for their informed consent. Consenting men and women of eligible couples will be asked to each fill out a questionnaire on expected live birth rate (Appendix 1) and the LOT-R questionnaire (Appendix 2) on general optimism.

**On the day of their fresh embryo transfer**, couples are randomized. Couples in the control group receive a document with a photo of their embryo(s) and the number of cryopreserved embryos. Couples in the intervention group receive a document with a photo of their transferred embryo(s), its quality rating, the number of cryopreserved embryos and couple's personalized IVF-prognosis (Appendix 5). Men and women of both groups will be asked to fill out the questionnaire on expected live birthrate (Appendix 1) and the STAI-state questionnaire on anxiety (Appendix 3).

**Within two days of the conclusive pregnancy test** after the transfers of the last (fresh or cryopreserved) embryo of the studied IVF-cycle, the IDS questionnaire on Patient's infertility-specific distress will be disseminated via text message and online (appendix 4).

**Eighteen months after the embryo transfer** of the last (fresh or cryopreserved) embryo of the studied IVF-cycle, the researchers will follow-up the long-term clinical and compliance outcomes in patient's medical chart (i.e. censored by their medical doctor to discontinue IVF, IVF-delay and IVF-discontinuation).

### 3.3 Withdrawal of individual subjects

Subjects can stop their participation in study at any time without having to give a reason. If this happens, only the data collected until that point will be used.

## 4. Data-analysis

### 4.1 Overall statistical considerations

The collected data will be imported into the 'Statistical Package for the Social Sciences (SPSS)'.

The previously proven reliability of the scales of the LOT-R, the STAI-state and the IDS will be re-evaluated by calculating Cronbach's alpha statistics and Item Total Correlations.

The collected data will be described with absolute values or percentages for categorical variables and with measures of dispersion (e.g. mean and standard deviation) for continuous variables, which is in line with the standard method of analysis of the used standardized LOT-R, STAI-state and IDS questionnaires.

The gathered data will be described separately for men and women. We will, however, explore whether partners differ in expected live birth rates, general optimism and infertility specific distress with paired t-tests. In addition, whether partner's influence each other regarding these three outcomes and whether this is affected by gender will be explored with linear mixed models.

A p-value  $\leq 0.05$  will be considered statistically significant.

### 4.2 IVF-live birth rates expected by patients

The IVF-live birth rates expected by patients will be analysed for both groups and for men and women separately. We will conduct an intention to treat analysis, primarily focussing on whether the intervention and the control group differ in the likeliness that women expect a live birth rate, which is at least twice as big as their prognosis. The difference in this binominal outcome will be analysed with a Chi-test. A p-value  $\leq 0.05$  will be considered statistically significant. To also inform readers about the extent of the potential difference, proportions of the primary outcome will be reported per group and the 95% confidence interval of the difference in proportions of the primary outcome between both groups (i.e. if significant, it will not include 0) will also be reported.

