Background variables	The following variables that potentially affect patient's expected live birth rate will be extracted from patient's medical file: whether they already had an ART-child (i.e. yes/no) and how many unsuccessful embryo transfers they had in the past (i.e. number). In addition, both partner's general optimism, will be assessed with the reliable questionnaire 'LOT-R' which will be disseminated in coded paper-pencil format on the day of oocyte aspiration.
Feasibility outcome	On the day of their fresh embryo transfer, men and women will be asked to fill out two questions on uptake and evaluation of the standardized personalized feedback.

Follow-up outcomes	Long-term clinical and compliance outcomes will be followed-up in couple's medical chart 12-18 months after the oocyte aspiration. More specifically, the 12-months cumulative clinical live birth rates for the observed oocyte aspiration will be extracted from the medical chart. In addition, the following compliance outcomes will be extracted: (i) censored by their medical doctor to discontinue IVF (yes-no) , (ii) number of untreated cycles within 12-months after oocyte aspiration and prior to the start of a new fresh cycle while not pregnant (i.e. IVF-delay), (iii) whether or not a subsequent IVF-cycle was started within twelve months after the last failed pregnancy test while not pregnant and no medical censoring to discontinue (i.e. IVF-discontinuation).
Study design	RCT (computerized randomization; 1/1 allocation sequence; no blinding)
Endpoints	The expected IVF live birth rate, anxiety and infertility specific distress of women and men.
Sample size	Hypothesizing that the intervention can lower the proportion of women expecting their live birth rate to be double their calculated IVF-prognosis from 50% to 25% dictates a sample size of 64 women per group (two-sided test; power 80%; $\alpha=0.05$ ; G*Power). To account for a 15% chance of study drop-out due to not filling-out the questionnaires or loss of follow-up, 74-80 women will be recruited per group .

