### 2.2 Study design

At the time of oocyte aspiration, patients will be randomised in two groups:

- Control group: At the time of their fresh embryo transfer couples will receive a document with a photo of their transferred embryo(s) and the number of cryopreserved embryos.
- Intervention group: At the time of their fresh embryo transfer couples will receive a document with the following feedback (Appendix 5): a photo of their transferred embryo, the number of cryopreserved embryos, the quality rating of the transferred embryo's (i.e. ★, ★★, ★★★, ★★★★, appendix 6), and couple's personalized IVF-prognosis (i.e. their chance on a live birth from the current IVF-cycle, including the transfer of fresh and if available cryopreserved embryos), calculated by entering eight background characteristics and five IVF-laboratory results into a prognostic model (Appendix 7).

Firstly, we wish to analyse whether personalized information on IVF-prognosis on the day of their fresh embryo transfer results in more realistic expected IVF-live birth rates.

Secondly, we wish to evaluate whether sharing these IVF-prognosis with patients at the time of embryo transfer is associated with the anxiety experienced by patients.

Thirdly, we wish to explore whether these IVF-live birth rates expected by patients are associated with the infertility specific distress experienced by patients at the time of a negative pregnancy test.

Fourthly, we wish to follow-up whether these IVF-live birth rates expected by patients are associated with clinical and compliance outcomes.

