### 2.3 Study parameters/endpoints

The **primary endpoint** is the proportion of women expecting directly after their fresh embryo transfer that their IVF-live delivery birth rate to be double their calculated IVF-prognosis (i.e. women's expected live birth rate  $\geq 2^* \text{prognose}$ ) In addition the proportion of men expecting their IVF-live birth rate to be double their calculated IVF-prognosis will be studied. Patient's expected IVF-live birth rates will be assessed immediately after the fresh embryo transfer with a single question coded paper-pencil questionnaire.

**Women's and men's anxiety** will be assessed with the reliable 'State-Anxiety Inventory, (STAI-state)' questionnaire disseminated in coded paper-pencil format on the day of the fresh embryo transfer (Appendix 3). The STAI-state questionnaire includes 20 questions rated on a-four-point-Likert scale and results in a score between 20 to 80 (the higher, the more anxiety).

**Patient's infertility-specific distress** will be assessed with the reliable 'Infertility Distress Scale (IDS)' questionnaire, which has been translated reciprocally to Dutch (Appendix 4). The IDS questionnaire will be disseminated via text message and online within two days of the conclusive pregnancy test after the transfers of the last (fresh or cryopreserved) embryo of the studied IVF-cycle. The IDS questionnaire includes eight questions to be rated on a-five-point-Likert scale and results in a score between 8 and 40 (the higher, the more infertility specific distress, Appendix 4).

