## Appendix 7: The thirteen factors which will be taken into account by the prognostic model

The prognostic model takes account of the following thirteen factors:

- female age
- duration of infertility
- previous ongoing live birth
- male subfertility
- diminished ovarian reserve
- endometriosis
- basal FSH
- number of failed IVF cycles
- fertilization in the previous IVF-cycle
- number of embryos in the current IVF-cycle
- mean morphological score per day 3 embryo in the current IVF-cycle
- presence of 8-cell embryos on day 3 in the current IVF-cycle
- presence of morulae on day 3 in the current IVF-cycle

The relative weight of the variables included in the Adapted van Loendersloot model		Background coding binary variabels	Adapted model		
Variables			Beta	Standard Error	P
Intercept			1.796	16.225	0.912
Couple characteristics	Age	-	0.023	1.499	0.988
	Age x age	-	0.000	0.046	0.998
	Age x age x age	-	0.000	0.000	0.947
	Duration of infertility (years)	-	-0.121	0.060	0.044
	Previous live birth (yes/no)	Yes=0; No=1	-0.061	0.167	0.715
	Male infertility (yes/no)	Yes=0; No=1	0.799	1.164	0.492
	Diminished ovarian reserve (yes/no)	Yes=0; No=1	0.250	0.312	0.423
	Endometriosis (yes/no)	Yes=0; No=1	0.265	0.190	0.163
	Basal FSH (IU/mL)	-	-0.130	0.082	0.114
	Number of previous failed IVF-cycles	-	-0.088	0.070	0.205
	Age x male infertility	-	0.028	0.034	0.409
	Endometriosis x Diminished ovarian reserve	Yes=0; No=1	-0.166	0.544	0.760
Current cycle characteristics	Embryo after ovum retrieval in the previous cycle (yes/no)	Yes=0; No=1	0.150	0.257	0.559
	Number of embryos after ovum retrieval	-	0.153	0.029	0.000
	Mean morphological score all embryos day three	-	-0.581	0.100	0.000
	Eight cell embryo on day three (yes/no)	Yes=0; No=1	-0.199	0.185	0.281
	Morulae on day three (yes/no)	Yes=0; No=1	-0.697	0.456	0.126

De formule waarmee de prognose wordt berekend:

$\text{Probability} = e^y / (1+e^y)$ 
Met
 $y = 1.796 + (0.023 * \text{Age}) + (-0.121 * \text{Duration of infertility}) + \dots + (-0.697 * \text{Morulae present on d3})$
--------------------------------------------------------------------------------------------------------------------------------------------------------------------------------------------------------------

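### The primary comparison in section 4.2 leaves out two covariates the trial already has; the chi-square is sound, and only precision is given up

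*Combined protocol and SAP*

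**What the plan says.** Section 4.2 gives the whole primary analysis: "The difference in this binominal outcome will be analysed with a" chi-square test, with the proportions per group and "the 95% confidence interval of the difference in proportions of the primary outcome between both groups". No covariate or stratification factor is named.

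The endpoint in section 2.3 is the "proportion of women expecting directly after their fresh embryo transfer that their IVF-live delivery birth rate to be double their calculated IVF-prognosis", defined as an expected rate of at least twice the prognosis. A prognosis is therefore needed for women in both groups. Appendix 7 lists its inputs: background data and current-cycle laboratory results such as "mean morphological score per day 3 embryo in the current IVF-cycle".

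Section 3.2 also collects the expectation question on the day of oocyte aspiration: "Consenting men and women of eligible couples will be asked to each fill out a questionnaire on expected live birth rate (Appendix 1"). Section 4 names no use for that aspiration-day answer.

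The time of randomisation is given twice, differently. Section 2.2: "At the time of oocyte aspiration, patients will be randomised in two groups". Section 3.2, for the day of fresh embryo transfer: "couples are randomized. Couples in the control group receive a document with a photo of their embryo(s".

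**The concern.** The endpoint compares a woman's expectation with a threshold that depends on her own prognosis, so prognosis can predict the endpoint. The Appendix 5 example of 38.39% needs an answer of at least 2 × 38.39 = 76.78%, and a woman whose prognosis is above 50% cannot be an event at all. An earlier answer to the same question is an obvious second predictor. Chance imbalance between the groups on either variable adds noise to a raw risk difference, and adjustment removes part of it.

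What is at stake is the width of the interval that section 4.2 promises, and some power. Neither the validity of the test nor bias is in question.

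**Working it through.** **1. The plan's own sample size.** Inputs (section 3.1.2): 50% against 25%, two-sided α = 0.05, power 80%, 64 per group. The pooled chi-square formula without continuity correction gives n = [1.960·√(2 × 0.375 × 0.625) + 0.842·√(0.25 + 0.1875)]² / 0.25² = 57.7, so 58 per group. With continuity correction it is 66. Full enumeration with Fisher's exact test gives 80.2% power at 64, which reproduces the stated figure.

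**2. Women likely to be scored per group.**
- Section 3.1.2 (80 recruited, 25% lost): 80 × 0.75 = 60.
- Synopsis ("To account for a 15% chance of study drop-out due to not filling-out the questionnaires or loss of follow-up", 74 to 80 recruited): 74 × 0.85 = 62.9, about 63; 80 × 0.85 = 68.

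**3. The planned test.** Exact power of the uncorrected chi-square is 81.8% at 60, 84.3% at 63, 84.9% at 64 and 86.3% at 68. Its exact type I error at 60 to 64 per group, for common rates of 25 to 50%, is about 4.5 to 5.8%. The test is valid and reaches 80%.

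**4. Width of the planned interval.** Half-width = 1.96·√[(0.25 + 0.1875)/n], which is 16.7 points at n = 60 and 15.7 at n = 68.

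**5. Possible gain, by simple algebra.** If the covariates explain a share R² of the outcome variance, the effective sample size is n/(1 − R²) and the standard error shrinks by 1 − √(1 − R²). From 60 per group, with asymptotic power 81.6% at R² = 0:
- R² = 0.1: 66.7 effective, SE 5% smaller, power 85.5%.
- R² = 0.3: 85.7 effective, SE 16% smaller, power 92.9%.
- R² = 0.5: 120 effective, SE 29% smaller, power 98.3%.

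The documents give no R², so these are assumptions.

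**6. Possible gain, by simulation of this endpoint.** All inputs are assumed. Logit prognosis is normal with median 20% or 30% and SD 0.35, 0.6 or 0.9 (0 to 17% of women above 50%). Logit expectation = a + k × (logit prognosis − its median) + 0.8 × noise, with k = 0, 0.5 or 1. The noise at the two visits correlates 0.3 or 0.7. The effect is either a logit shift or half the women adopting the prognosis they are told, calibrated to 50% and 25%. That makes 2 × 3 × 3 × 2 × 2 = 72 scenarios, with 2,000 trials each.

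| | 60 per group | 68 per group |
|---|---|---|
| Both covariates: SE smaller by | 2.8 to 27.5% | 1.4 to 28.0% |
| 95% half-width, points | 12.1 to 16.3 | 11.3 to 15.5 |
| Power | 83 to 98% | 86 to 99% |
| SE reduction when k = 1 and correlation 0.3 | 2.8 to 13.7% | 1.4 to 15.0% |
| SE reduction with 15% of aspiration answers missing, mean-imputed | 2.2 to 26.7% | 1.3 to 27.2% |
| Prognosis only: SE reduction | −0.3 to 23.8% | 0.0 to 25.7% |
| Prognosis only: power | 80 to 97% | 85 to 98% |

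Adjusted and raw estimates averaged within 0.4 points of each other in every scenario. Under the null, type I error averaged 4.8% adjusted against 5.6% for the chi-square at 60 per group, and 4.8% for both at 68. A smaller set of 20 repeat runs at 60 per group gave SE reductions of about 0 to 25% with both covariates and 0 to 21% with prognosis alone.

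**The case against.** The strongest reply is that this is a preference. An unadjusted chi-square with a risk difference and interval is prespecified, transparent and of the same type as the sample-size calculation. That is true, and it is why the point is an improvement only.

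Second, the size of the gain is wholly assumed. The largest reductions need widely spread prognoses, expectations unrelated to prognosis and a strong correlation between the two answers. This stands: neither the upper end nor a midpoint should be quoted as the expected benefit.

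Third, the aspiration-day answer may predict weakly. Appendix 1 refers to the current fresh transfer, and at aspiration the embryo results do not yet exist. Only section 3.2 places the question on that day; the synopsis mentions only the optimism questionnaire there. This also stands, and the lower correlation of 0.3 is in the range for that reason.

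Fourth, if randomisation is at aspiration, the laboratory inputs to prognosis also follow allocation in an open trial, so dropping only the aspiration-day answer looks uneven. The two differ, however. Knowing the allocation could sway an answer, whereas the feedback sheet cannot change embryo results, and prognosis is already part of the endpoint. At its low end the prognosis-only fallback shows no benefit: 80% power at 60 per group against 81.8%. With 2,000 trials the Monte Carlo error is √(0.8 × 0.2/2000) = 0.9 points, and the chi-square's own type I error there is slightly above 5%.

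Finally, the 80% power holds for the uncorrected chi-square. With continuity correction it is 76.0% at 60, 79.3% at 63 and 79.9% at 64, and section 4.2 does not say which version applies. That qualifies the reassurance about power and does not weaken the case for adjusting.

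**Conclusion.** The point holds as an improvement to the plan. The primary comparison is unadjusted although two plausible predictors are already collected or calculated in both groups. The chi-square is valid and, uncorrected, meets 80% power at 60 to 68 scored women per group.

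What is given up is precision: somewhere between almost nothing and about 28% of the standard error, under assumed distributions and correlations that the documents neither confirm nor exclude. In the simulated scenarios adjustment did not materially move the estimate or inflate the type I error, and at worst it left precision practically unchanged. Use of the aspiration-day answer depends on its being given before allocation, which the protocol leaves open.

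**What to change.** 1. Reconcile sections 2.2 and 3.2 on the time of randomisation, and confirm that the Appendix 1 question is answered at aspiration before allocation.
2. In section 4.2, prespecify as the primary estimate and test the risk difference between groups adjusted for aspiration-day expectation and prognosis. Linear regression with HC3 robust standard errors does this. A logistic model standardised to a marginal risk difference is an alternative, but one method must be named in advance. Either keeps the scale on which section 4.2 already reports.
3. Keep every scored woman by replacing a missing aspiration-day answer with the overall mean of that covariate.
4. Report the raw proportions, the chi-square (stating whether it is continuity-corrected) and the unadjusted interval as a sensitivity analysis.
5. If the aspiration-day answer cannot be assured to precede allocation, adjust for prognosis only.

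The cost is one paragraph in section 4.2 and the reconciliation, with no new data and no change in sample size. The downside is that the headline becomes a model-adjusted difference instead of a plain two-by-two comparison, for a gain that may be close to zero. The choice should be fixed before any outcome data are analysed, because in an open trial covariates chosen afterwards would invite criticism.

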### 4.3 Quantification of the under/over estimation of the live birth rates expected by patients

In addition to the primary outcome (i.e. evaluating the proportion of women expecting their IVF-live birth rate to be double their calculated IVF-prognosis directly after their fresh embryo transfer) we want to quantify this under/over estimation. This will be calculated using the following formula: (expected LBR-prognosis)/prognosis. A positive sign shows overestimation, a negative sign shows underestimation and the absolute value quantifies the extend of the over/underestimation. For both groups, the mean and SD will be calculated. In addition, the mean difference in misjudgement between both groups and its 95% confidence interval (i.e. to give an impression of the preciseness of this estimation) will be reported.

### 4.4 Anxiety experienced by patients

Whether the intervention and control group, differ in anxiety on the day of their embryo transfer will be analysed by comparing both groups STAI-state with an independent sample t-test. A p-value  $\leq 0.05$  will be considered statistically significant and the mean difference in anxiety between both groups and its 95% confidence interval will be reported.

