### 4.5 Association between patient's general optimism and their expected live birth rates

Furthermore, we will assess in the entire sample with linear mixed models including 'couple number' as a random factor to take account of clustering within couples, if patient's general level of optimism is associated to their expected live birth rate.

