### 4.6 Association between IVF-live birth rates expected by patients and infertility specific distress

Whether the intervention and control group, differ in infertility specific distress on the day of their embryo transfer will be analysed by comparing both group's IDS-score with an independent sample t-test. A p-value  $\leq 0.05$  will be considered statistically significant and the mean difference in infertility specific distress between both groups and its 95%

confidence interval will be reported. In addition, a linear (mixed or non-mixed) model will explore in the entire sample whether IVF-live birth rates expected by patients are associated with their infertility specific distress. We will examine whether gender significantly ( $p \leq 0.05$ ) affects the association between the IVF-live birth rate expected by patients and their infertility specific distress. If it does, we will rely on linear (non-mixed) models per gender. If it does not, we will rely on linear mixed models while including 'couple number' as a random factor to take account of clustering within couples, as partners cannot be considered independent cases.

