### 6.2 Recording of adverse events

Safety events will be recorded from informed consent signature until the day of their last embryo transfer. This study does not affect couple's treatment and we do not expect physical risks from giving patients their personalized prognosis. The personalized prognosis might, however, increase anxiety on the day of embryo transfer and this will be monitored with a validated questionnaire during the study. In addition, participant's reports of distress, potentially made to medical doctors during embryo transfer or reported on the questionnaire administered directly after the transfer will be registered.

The participant will be asked to report any adverse event related to the study-specific intervention to the study team. These reported events will be documented by the Investigator in the source documents. The following minimum information should be recorded for each AR:

- AE description of the adverse events
- Start and stop date of the AR
- Severity
- Seriousness
- Causality assessment to the study interventions
- Outcome

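### Section 4.4 compares transfer-day anxiety by an unadjusted t-test; a pre-specified ANCOVA on the LOT-R already being collected could narrow the interval, by an amount that depends on an unknown correlation

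*Combined protocol and SAP*

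**What the plan says.** Section 4.4 compares STAI-state between arms on the day of embryo transfer: the difference "will be analysed by comparing both groups STAI-state with an independent sample t-test", reported as a mean difference with its 95% confidence interval. No covariate is named. Section 4.6 treats infertility-specific distress in the same way, "comparing both group's IDS-score with an independent sample t-test".

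Under section 3.2, consenting men and women are asked at aspiration to complete a questionnaire on expected live birth rate "and the LOT-R questionnaire (Appendix 2) on general optimism". The synopsis agrees that the LOT-R is "disseminated in coded paper-pencil format on the day of oocyte aspiration". It lists the scale among "variables that potentially affect patient's expected live birth rate" and states no link to anxiety or distress. Section 4.5 models "if patient's general level of optimism is associated to their expected live birth rate". Section 4.1 adds a reliability check, paired comparisons between partners, and mixed models of partner influence. None of these uses concerns anxiety.

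Section 6.2 says: "The personalized prognosis might, however, increase anxiety on the day of embryo transfer". It relies on the anxiety questionnaire to monitor this. No STAI-state is scheduled before feedback.

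**The concern.** Section 4.4 is the between-arm analysis of the harm that the protocol itself foresees. The sample size in section 3.1.2 was set for the primary proportion, and the documents give no SD, target difference or power for STAI-state. The anxiety interval will therefore be as wide as that sample size leaves it, and a wide interval that includes zero is easily read as reassurance.

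The usual remedy, adjustment for a baseline value of the same scale, is not available because no STAI-state is taken before feedback. The LOT-R is the validated psychological scale that is taken then, and feedback given at transfer cannot change an answer already given. If optimism is related to state anxiety, leaving the LOT-R out of the model gives up precision that the trial has already collected. It also leaves any chance difference in optimism between the arms uncorrected in the estimate.

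**Working it through.** **Inputs from the documents.** Section 3.1.2: 64 women per group, two-sided alpha 0.05, power 80%, 50% versus 25% on the primary outcome. Section 2.5: 1:1 allocation. Section 2.3: STAI-state runs from 20 to 80; no SD is given, so results are in SD units.

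**Assumed.** The within-arm correlation r between LOT-R and STAI-state (0 to 0.5), and, for the power column only, a true difference of 0.3 SD.

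**The plan's own figure.** Fisher's exact test for 50% versus 25% has power 79.4% at 63 per group and 80.2% at 64, so 64 reproduces. It is a figure for the binary primary outcome and not for anxiety.

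**Order of measurement.** Section 2.2 places randomisation at aspiration and section 3.2 places it on the day of transfer. On either reading the LOT-R precedes the feedback, which is given only at transfer.

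**Unadjusted t-test, n = 64 per arm.**
Half-width = t(0.975; 126) × √(2/64) = 1.979 × 0.1768 = 0.350 SD. Power for a 0.3 SD difference (non-central t) is 39.1%.

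**ANCOVA with one covariate.** The residual SD is √(1 − r²) times the raw SD, one degree of freedom is lost, and the expected cost of chance imbalance in the covariate is a factor √(1 + 1/(2n − 4)):

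Half-width = t(0.975; 125) × √(2/64) × √(1 + 1/124) × √(1 − r²) = 1.979 × 0.1768 × 1.0040 × √(1 − r²) = 0.3513 × √(1 − r²).

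| Assumed r | √(1 − r²) | Half-width (SD) | Change from 0.350 | 64/(1 − r²) per arm | Power at 0.3 SD |
|---|---|---|---|---|---|
| 0 | 1.000 | 0.351 | 0.4% wider | 64 | 38.9% |
| 0.1 | 0.995 | 0.350 | 0.1% narrower | 65 | 39.2% |
| 0.2 | 0.980 | 0.344 | 1.6% narrower | 67 | 40.2% |
| 0.3 | 0.954 | 0.335 | 4.2% narrower | 70 | 42.0% |
| 0.4 | 0.917 | 0.322 | 8.0% narrower | 76 | 44.8% |
| 0.5 | 0.866 | 0.304 | 13.0% narrower | 85 | 49.1% |

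The fifth column is the approximate number per arm that an unadjusted analysis would need for the same residual variance; it ignores the two small costs. Break-even lies at r of about 0.09.

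**Chance imbalance.** The between-arm difference in mean LOT-R has a standard error of √(2/64) = 0.177 SD. An imbalance at the edge of its 95% range (1.96 × 0.177 = 0.35 SD) would shift the unadjusted anxiety difference by r × 0.35 SD: about 0.10 SD at r = 0.3 and 0.17 SD at r = 0.5.

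**The case against.** The strongest reply is that nothing is wrong. In a randomised comparison the t-test is valid and unbiased, and its interval already allows for chance imbalance in optimism. That stands.

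A reader might go further than the point does in four ways, and the documents support none of them.

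- One might infer that the planned comparison *is* less precise than the data allow. That needs a LOT-R/STAI-state correlation of some size. The documents give none, and they justify the LOT-R only by its possible link to expected live birth rate. Below about r = 0.09 there is no gain.
- One might call the adjustment free. It costs a degree of freedom and widens the interval by 0.4% if r = 0.
- One might think the LOT-R is used nowhere but in 4.5, or is the only questionnaire answered before feedback. Section 4.1 also uses it, and expected live birth rate is asked at aspiration as well. Nor is every LOT-R sure to be complete: partners are asked to fill it in, and the sample size allows for unfilled questionnaires.
- One might carry the harm argument over to the IDS. Section 6.2 is about anxiety on the day of transfer, whereas sections 2.3 and 3.2 send the IDS after the pregnancy test that follows the last transfer.

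It is also fair to say that adjustment does not cure the limited precision: power for an assumed 0.3 SD difference stays below 50% in every row of the table. What survives is narrower. The possible loss is negligible, the possible gain is useful, and the covariate is already in hand.

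**Conclusion.** The point holds as a low-cost improvement to section 4.4, not as the correction of an error. At 64 per arm, pre-specified adjustment for LOT-R would change the 95% half-width for anxiety from 0.350 SD to between 0.351 SD (r = 0) and 0.304 SD (r = 0.5), with 0.335 SD at r = 0.3. The gain is modest unless r reaches about 0.4.

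These figures rest on the assumed r, on a linear relation with equal variance in both arms, and on 64 analysed women per arm. For men they apply only if the same number respond. For the IDS the argument is one of precision alone, and neither a correlation nor an expected number of respondents is available for it.

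**What to change.** **Section 4.4.** Make the main analysis a linear model, fitted separately for women and men, with arm and the person's own LOT-R total as covariate. Report the adjusted mean difference with its 95% confidence interval. Replace a missing LOT-R total by the mean for that gender pooled over both arms, so that nobody with a STAI-state score is dropped. Keep the independent-sample t-test as a sensitivity analysis. Fix all of this before outcome data are seen, because a covariate chosen afterwards invites selective reporting.

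**Section 4.6.** The same model may be used for the IDS. First reconcile the timing: 4.6 speaks of distress on the day of embryo transfer, while 2.3 and 3.2 place the IDS after the conclusive pregnancy test.

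**Cost.** A few sentences in 4.4, optionally one in 4.6, and no new data. The statistical downside is one degree of freedom and a negligible loss of precision if the correlation is near zero.
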